### **Subject Data Listings – Safety Population**

#### **Discontinued Subjects**

- Listing 16.2.1.1.1 Subject Disposition (Completion or Discontinuation) & Compliance
- Listing 16.2.1.1.2 Subject Disposition (visit dates)
- Listing 16.2.1.2 Discontinued Subjects: Adverse Events

### **Protocol Deviations – Safety Population**

- Listing 16.2.2.1 Listing of Protocol Deviations
- Listing 16.2.2.2 Eligibility: Inclusion/Exclusion Criteria

## **Subjects Excluded from the Efficacy Analysis**

Listing 16.2.3.1 Listing of Subjects Excluded from the Efficacy Analysis

## **Demographic and Baseline Characteristics Data – Safety Population**

Listing 16.2.4.1 Demographics and Baseline Characteristics

Listing 16.2.4.2 Medical History and Hyperhidrosis History

Listing 16.2.4.3 Prior and Concomitant Medications

## **Compliance and/or Drug Concentration Data – Safety Population**

Listing 16.2.5.1 Investigational Product Accountability

Listing 16.2.5.2 Investigational Product Exposure

## **Individual Efficacy Response Data – Safety Population**

Listing 16.2.6.1 Efficacy HDSM-Ax and HDSM-Ax, Child at Baseline and Change from Baseline

Listing 16.2.6.2 Efficacy PGI-S at Baseline and Change from Baseline

## **Adverse Event Listings (each Subject) – Safety Population**

Listing 16.2.7.1 Adverse Event Listing

Listing 16.2.7.2 Serious Adverse Event Listing

Listing 16.2.7.3 Vital Signs

Listing 16.2.7.4 ECGs

Listing 16.2.7.5 ECG Abnormalities

Listing 16.2.7.6 Physical Examination

Listing 16.2.7.7 Application site burning, itching, dryness, scaling and erythema

## **Listing of Individual Laboratory Measurements by Subject - Safety Population**

Listing 16.2.8.1 Clinical Chemistry Laboratory Measurements

Listing 16.2.8.2 Hematology Laboratory Measurements

Listing 16.2.8.3 Urinalysis Laboratory Measurements

Listing 16.2.8.3 Drug and Alcohol Screen

Listing 16.2.8.4 Pregnancy Testing

## **Other Data Listings – Safety Population, patients with respective comments**

Listing 16.2.9.1 Case Report Form General Comments

Listing 16.2.9.2    Laboratory Data Comments

Listing 16.2.9.3    ECG Data Comments

## 15.2 Appendix B: Preliminary Table of Contents for Tables, Listings, Figures for PK Tables

Table 14.x.x.1 Summary of Mean (SD), CV%, Median, Min and Max Sofpironium Plasma Concentrations (Ctrough values) by Week

Table 14.x.x.2 Summary of Mean (SD), CV%, Median, Min and Max Metabolite Plasma Concentration (Ctrough values) by Week

## Listings

Listing 16.x.x.1 Individual Pharmacokinetic Sampling Times and Plasma Concentrations (Ctrough) values of Sofpironium by Week

Listing 16.x.x.2 Individual Pharmacokinetic Sampling Times and Plasma Concentrations (Ctrough) of Primary Metabolite by Week

## Figures

### Table of Content for Figures

Figure 14.x.x.1 Mean ( $\pm$ SD) Sofpironium Plasma Concentrations (Ctrough) versus Week (Linear Scale)

Figure 14.x.x.2 Mean ( $\pm$ SD) Primary Metabolite Plasma Concentrations (Ctrough) versus Week (Linear Scale)

Figure 14.x.x.3 Overlaid Individual Sofpironium Plasma Concentrations (Ctrough) versus Week (Linear Scale)

Figure 14.x.x.4 Overlaid Individual Primary Metabolite Plasma Concentrations (Ctrough) versus Week (Linear Scale)

### 15.3 Appendix C: HDSM-Ax, Child ( $\geq 9$ to $<12$ years of age)

#### HDSM-AX CHILD (VERSION 28 FEB 2018)

**INSTRUCTIONS:** We are interested in finding out about your underarm sweating.

- Circle the best answer to each question.
  - Think about sweating in your **underarms only**.
  - Think about your sweating **this morning and yesterday**.
- Please answer **ALL** questions.

---

1. Since you woke up yesterday, how often did you have these things?

	None of the time	A little of the time	Some of the time	Most of the time	All of the time
a) Damp or wet clothes from underarm sweating ?	0	1	2	3	4
b) Underarm sweating for no reason?	0	1	2	3	4

2. Since you woke up yesterday, how much did you have these things?

	I did not have this	A tiny amount	A little	A lot	A great amount
a) Underarm sweating when you felt nervous, scared, or worried?	0	1	2	3	4
b) Damp or wet clothing from underarm sweating ?	0	1	2	3	4
c) Underarm sweating after sitting quietly?	0	1	2	3	4
d) Underarm wetness?	0	1	2	3	4
e) Underarm sweating for no reason?	0	1	2	3	4
f) Underarm sweating that you could not hide?	0	1	2	3	4
g) Underarm sweating when you were not hot?	0	1	2	3	4

PROPRIETARY AND CONFIDENTIAL

3. Since you woke up yesterday, how much did you want to do these things?

	Not at all	A tiny amount	A little	A lot	A great amount
a) Change clothes because of underarm sweating ?	0	1	2	3	4
b) Wipe sweat from your underarms ?	0	1	2	3	4

4. Since you woke up yesterday, how much of the time did you have underarm sweating?

- 0 None of the time
- 1 A little of the time
- 2 Some of the time
- 3 Most of the time
- 4 All of the time

5. Describe your underarm sweating AT ITS WORST since you woke up yesterday?

- 0 I did not have underarm sweating
- 1 I had a tiny amount of underarm sweating
- 2 I had some underarm sweating
- 3 I had a lot of underarm sweating
- 4 I had a great amount of underarm sweating

**6. Patient Global Impression of Severity (PGI-S)**

**Please choose the response below that best describes the severity of your underarm sweating over the past week.**

- None
- Mild
- Moderate
- Severe
- Very severe

**7. Patient Global Impression of Change (PGI-C)**

**Please choose the response below that best describes the overall change in your underarm sweating since you started taking the study medication.**

- Very much better
- Moderately better
- A little better
- No change
- A little worse
- Moderately worse
- Very much worse

## 15.4 Appendix D: HDSM-Ax ( $\geq 12$ years of age)

HDSM-Ax Version 1.3

### Hyperhidrosis Disease Severity Measure--Axillary® (HDSM-Ax)

**INSTRUCTIONS:** We are interested in finding out about your current experience with excessive underarm sweating.

- Please consider excessive sweating in your **underarms only** when selecting the answer to each question.
- For each statement, please provide the response that best describes your **experience since you woke up yesterday**.
- Please answer **ALL** questions even if some seem similar to others or seem irrelevant to you.

1. Since you woke up yesterday, how often did you experience the following while you were awake? (Please select the number that best describes your experience.)

	None of the time	A little of the time	Some of the time	Most of the time	All of the time
a) Damp or wet clothing caused by underarm sweating ?	0	1	2	3	4
b) Underarm sweating for no apparent reason?	0	1	2	3	4

2. Since you woke up yesterday, how severe was your experience with the following? (Please select the number that best describes your experience.)

	I did not experience this	Mild	Moderate	Severe	Very severe
a) Underarm sweating when you felt nervous, stressed or anxious?	0	1	2	3	4
b) Damp or wet clothing caused by underarm sweating ?	0	1	2	3	4
c) Underarm sweating after little or no physical exercise?	0	1	2	3	4
d) Underarm wetness?	0	1	2	3	4
e) Underarm sweating for no apparent reason?	0	1	2	3	4
f) Underarm sweating that was unmanageable?	0	1	2	3	4
g) Underarm sweating when you were cool?	0	1	2	3	4

HDSM-Ax Version 1.3

3. Since you woke up yesterday, what was your experience with each of the following? (Please select the number that best describes your experience.)

	Not at all	Slight	Moderate	Strong	Very strong
a) Feeling the need to change clothes because of underarm sweating?	0	1	2	3	4
b) Feeling the need to wipe sweat from your underarms?	0	1	2	3	4

4. Since you woke up yesterday, how much of the time did you experience excessive underarm sweating while you were awake? (Please select the number that best describes your experience.)

0      None of the time  
1      A little of the time  
2      Some of the time  
3      Most of the time  
4      All of the time

5. How severe was your underarm sweating AT ITS WORST since you woke up yesterday? (Please select the number that best describes your experience.)

0      I did not have underarm sweating (i.e., completely dry)  
1      I had underarm sweating but it was mild (i.e., slightly damp)  
2      I had underarm sweating and it was moderate (i.e., damp)  
3      I had underarm sweating and it was severe (i.e., wet)  
4      I had underarm sweating and it was very severe (i.e., soaking)

*HDSM-Ax Version 1.3*

**6. Patient Global Impression of Severity (PGI-S)**

**Please choose the response below that best describes the severity of your underarm sweating over the past week.**

- None
- Mild
- Moderate
- Severe
- Very severe

**7. Patient Global Impression of Change (PGI-C)**

**Please choose the response below that best describes the overall change in your underarm sweating since you started taking the study medication.**

- Very much better
- Moderately better
- A little better
- No change
- A little worse
- Moderately worse
- Very much worse

## 15.5 Appendix E: Application Site Tolerability Assessments

These assessments are to be performed for each axilla individually. The designation of “Right Axilla” or “Left Axilla” in the source documents and eCRFs refers to the subject’s right and left axilla respectively in all cases. Subject assessments are to be performed prior to Investigator assessments.

**Local Tolerability (Subject):** As reported by the Subject to the Investigator, the severity of any symptoms of burning, stinging or itching at the application-site within the previous 24 hours and further any such symptoms persisting longer than 1 hour following study drug application will be described specifically by severity using the following standardized scales:

Score	Burning	Stinging	Itching
0 = Absent	Normal, no discomfort	Normal, no discomfort	Normal, no discomfort
1 = Minimal	An awareness, but no discomfort	An awareness, but no discomfort	An awareness, but no discomfort
2 = Mild	Noticeable discomfort causing intermittent awareness	Noticeable discomfort causing intermittent awareness	Noticeable discomfort causing intermittent awareness
3 = Moderate	Noticeable discomfort causing continuous awareness	Noticeable discomfort causing continuous awareness	Noticeable discomfort causing continuous awareness
4 = Severe	Definite discomfort causing continuous awareness, interfering occasionally with normal daily activities	Definite discomfort causing continuous awareness, interfering occasionally with normal daily activities	Definite discomfort causing continuous awareness, interfering occasionally with normal daily activities

**Local Tolerability (Investigator):** The Investigator will assess the drug-application site for the existence of significant local symptoms. Significant local symptoms are defined as those not ordinarily observed following application of a topical product. The following standardized scales will be used to describe specifically the severity of any erythema or scaling:

Score	Scaling	Erythema
0 = Absent	No scaling	No redness
1 = Minimal	Fine scaling, barely perceptible	Faint red or pink coloration, barely perceptible
2 = Mild	Slight scaling, noticeable only with light scratching	Light red or pink coloration
3 = Moderate	Definitely noticeable scaling	Medium red coloration
4 = Severe	Extensive scaling	Beet red coloration

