6.6 Application Site Tolerability Assessment

Application site tolerability assessments will be evaluated through assessment of symptoms at the drug-application site. These assessments are to be performed for each axilla individually. Subject assessments will be made prior to the Investigator assessments ([Appendix F](#)).

Subject Local Tolerability Assessments: Subjects will be queried about whether any symptoms of burning, stinging, or itching occurred at the drug-application site within the previous 24 hours and further whether any such symptoms persisted longer than 1 hour following study drug application. Standardized scales will be used to describe specifically the severity of any burning, stinging or itching ([Appendix F](#)).

Investigator Local Tolerability Assessments: Investigators will observe for the existence of any significant local symptoms of scaling or erythema at the drug-application site. Significant local symptoms are defined as those not ordinarily observed following application of a topical product. Standardized scales will be used to describe specifically the severity of any erythema or scaling ([Appendix F](#)).

Local tolerability signs and symptoms that result in the subject's requiring a concomitant therapy, interruption of treatment, or discontinuation from the study, will also be reported as an AE.

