11.3.3 Treatment Compliance

The subject or parent(s)/guardian(s) will record the date and time of all applications made to the right and left axilla or missed applications in the dosing diary card. Subject compliance during the overall treatment period and by visit will be summarized.

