## 7.2 Endpoints

### 7.2.1 Primary Endpoints

#### 7.2.1.1 Safety

- Incidence and severity of application site burning, itching, stinging, scaling and erythema
- Incidence and severity of all AEs and their relationship to study drug
- Incidence of clinically meaningful change from baseline in safety laboratory parameters, physical examination, 12-lead ECGs and vital signs
- Proportion of subjects who discontinue treatment due to an AE

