### 13.3 Primary Analyses

#### 13.3.1 Safety

Safety evaluations will consist of AEs, application site local tolerability, physical examinations, vital signs, ECGs, and laboratory measurements (hematology, chemistry, and urinalysis).

- Adverse events:
  - Adverse events will be mapped to standard terms, i.e., MedDRA System Organ Class and Preferred Term.
  - Adverse events that occurred during the screening period will be listed separately and will not be included in the AE tabulations.
  - Adverse events that start on or after first dose will be considered a TEAE. At each post-baseline visit, the number and proportion of subjects reporting any given TEAE will be tabulated by severity; each subject will be counted only once according to the worst severity reported up to the current visit. Separate tables will be constructed for (a) all reported TEAEs, (b) protocol treatment related TEAEs, (c) serious TEAEs, and (d) TEAEs leading to protocol treatment discontinuation.
- At each applicable visit, local tolerability (burning, itching, stinging, scaling, and erythema at either axilla) will be described by severity as defined in Appendix E. Subject and Investigator assessments will be included in separate tables and listings, with the count and percentage of subjects within each severity (maximum severity assessed at either axilla) presented by parameter and visit.
- Vital signs will be summarized similarly as for laboratory parameters but without shift tables.
- Laboratory parameters will be descriptively summarized (mean, SD, median, minimum, maximum) for values at each visit and for changes from baseline at each subsequent visit. In addition, at each post baseline visit, parameter status (low, normal, high) will also be summarized as shift tables vs. baseline status.
- Descriptive statistics and/or frequency tables will be prepared as appropriate for physical examinations, and ECG (HR, QTcF, PR, and QRS) parameters, and abnormalities (e.g., normal; abnormal, not clinically significant; abnormal, clinically significant).
- Concomitant medications will be mapped according to the World Health Organization Drug Dictionary (WHODD) and will be presented in data listings.

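### Burning, stinging and itching are tabulated by visit whether or not gel was applied in the 24-hour recall window, so an undosed subject can count as Absent in a primary endpoint

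*SAP*

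**What the plan says.** The first primary safety endpoint in SAP 7.2.1.1 is "Incidence and severity of application site burning, itching, stinging, scaling and erythema". The five items are rated in two ways (SAP 15.5, Appendix E; the same in Protocol 6.6 and Appendix F).

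- **Burning, stinging, itching.** The subject reports "the severity of any symptoms of burning, stinging or itching at the application-site within the previous 24 hours". A second part of the question is tied to an application and covers "any such symptoms persisting longer than 1 hour following study drug application". Score 0 (Absent) reads "Normal, no discomfort". Neither document says how to rate if there was no application in that time.
- **Scaling, erythema.** "The Investigator will assess the drug-application site for the existence of significant local symptoms". These are observed at the visit and have no 24-hour window.

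SAP 13.3.1 puts subject and investigator ratings in separate tables, "with the count and percentage of subjects within each severity (maximum severity assessed at either axilla) presented by parameter and visit". The analysis set is the Safety population (SAP 12.1 and 12.3.1), for which one application at any time and one later safety assessment suffice.

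The protocol foresees subjects attending while off drug. Section 10.2.3 has an interruption code under action taken, and section 4.5.1.1 keeps subjects who have stopped treatment in the visit schedule. SAP 12.5 files the early-termination visit under Visit 7 (Week 24).

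Two further provisions matter. Under Protocol 6.6, local signs and symptoms "requiring a concomitant therapy, interruption of treatment, or discontinuation from the study, will also be reported as an AE". Under Protocol 11.3.3, the subject or parent "will record the date and time of all applications made to the right and left axilla or missed applications in the dosing diary card", and SAP 13.2 has applications made or missed entered in the eCRF.

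**The concern.** A rating of zero can mean two things: gel was applied and caused no symptoms, or no gel was applied and there was nothing to cause them. The planned table does not separate the two. Both fall in the Absent row and both stay in the denominator.

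The undosed subjects need not be a random subset, because irritation is one reason to skip or pause. If they are disproportionately those who react, the by-visit percentages understate how the gel is tolerated by people using it. The table has no worst post-baseline summary to hold on to an earlier high score. Summary tables also leave out unscheduled visits (SAP 12.3.1), so a reaction scored at an unscheduled visit and followed by a pause could appear in the tolerability table only as a later scheduled zero.

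At stake is the reading of a primary endpoint in a small paediatric safety study whose purpose is to describe long-term tolerability.

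**Working it through.** The plan has no figure to reproduce. The analysis is descriptive, and the maximum of 24 subjects comes from the parent study (SAP 11). The check uses simple proportions to see how far the table could move.

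**Inputs**
- N = 24, the maximum (SAP 11).
- k = subjects at a visit with no application in the window. Assumed, since the documents give no rate.
- x = subjects dosed in the window who report a symptom. Assumed, for the same reason.
- Undosed subjects are taken to score 0. This is the unfavourable case, because symptoms that linger into the window would still be scored.

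**Formulas**
- Planned table: x / 24
- Dosed subjects only: x / (24 − k)
- If all k had stopped because of symptoms and these are counted: (x + k) / 24

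**Results for x = 4**

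| k | Planned table | Dosed only | Counting the k as reactors |
|---|---|---|---|
| 1 | 4/24 = 16.7% | 4/23 = 17.4% | 5/24 = 20.8% |
| 2 | 16.7% | 4/22 = 18.2% | 6/24 = 25.0% |
| 4 | 16.7% | 4/20 = 20.0% | 8/24 = 33.3% |
| 6 | 16.7% | 4/18 = 22.2% | 10/24 = 41.7% |

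One subject is 1/24 = 4.2 percentage points.

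**Doses missed for unrelated reasons.** If a proportion p of dosed subjects report a symptom and a proportion q are undosed and score 0, the table shows p(1 − q). With p = 25% assumed:
- q = 10%: 0.25 × 0.90 = 22.5%, a shortfall of 24 × 0.025 = 0.6 of a subject.
- q = 25%: 0.25 × 0.75 = 18.75%, a shortfall of 24 × 0.0625 = 1.5 subjects.

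**Doses paused because of the reaction.** Suppose 6 of 24 react and 3 of them are paused at the visit. The planned table shows 3/24 = 12.5%, while 6/24 = 25% have reacted. Restricting the table to dosed subjects gives 3/21 = 14.3%. That barely moves toward 25%, because the paused reactors leave both numerator and denominator.

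Dilution from unrelated missed doses is therefore small. Reaction-driven pauses can matter more, and a dosed-only table does not recover them.

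**The case against.** The strongest reply is that a pause caused by irritation is already captured. Protocol 6.6 makes it an AE, SAP 13.3.1 counts each subject in the TEAE tables at the worst severity to date, and AE incidence and severity is itself a primary endpoint. Protocol 4.5.1.1 also requires permanent discontinuation for an adverse reaction to the drug, which narrows the group that pauses for irritation and later resumes. A reader might infer that reactors vanish from the primary safety data. The documents do not support that.

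The safeguard has limits. It does not alter the tolerability table. AEs are graded on three levels and tolerability from 0 to 4, so one display does not stand in for the other. SAP 13.3.1 plans a TEAE table for discontinuation but none for interruption. Doses skipped because of stinging, without a recorded interruption or concomitant therapy, need not become an AE at all.

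A second reply is that the table correctly reports what attending subjects said at each visit, which is a legitimate quantity. This stands: visit prevalence and risk while on drug are different things, and the 25% in the last example is the second. The problem is that the table does not let the reader tell them apart.

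A third reply is that the listings allow a check by hand. SAP 13.2 summarises applications by day and visit, and Appendix A plans exposure and tolerability listings. With at most 24 subjects this is feasible, but it leaves the reader to do the derivation. The title of Listing 16.2.7.7 also does not name stinging.

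**Conclusion.** The concern holds for three of the five items. A subject who attends without having applied gel in the previous 24 hours and has no symptoms enters a primary-endpoint table as Absent, with nothing to mark the lack of exposure. This can bias the by-visit burning, stinging and itching rates downward.

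The size is unknown. Each affected subject moves a rate by about 4 percentage points at N = 24. In the illustrations, 16.7% compares with 17.4% to 20.0% among dosed subjects for one to four undosed, and with 20.8% to 33.3% if those subjects stopped because of symptoms. All of this rests on assumed k and x and on undosed subjects scoring 0.

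Three stronger readings are tempting and not supported:
- That every undosed subject counts as Absent. Appendix E asks about any symptoms in the window, dose or no dose, so lingering irritation is scored.
- That scaling and erythema share the recall problem. They have no 24-hour window.
- That tolerability will appear to improve over 24 weeks. It could, if reactors skip doses around visits, but no figure in the documents shows that they do, and the cumulative TEAE count would not show such an improvement.

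This is an inexpensive improvement to how a primary endpoint is displayed. It does not show that the planned safety analysis misses the events.

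**What to change.** In SAP 13.3.1, for burning, stinging and itching:

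1. Keep the all-subjects by-visit table.
2. Derive from diary dates and times whether gel was applied in the 24 hours before each rating. If the clock time of the rating is not on the eCRF, use the application recorded for the previous evening.
3. Show dosed and not-dosed subjects separately, with the severity scores of both. Give the reason for not dosing: missed, interrupted or discontinued for a local reaction, other, or diary missing. The AE action-taken field identifies interruptions and withdrawals due to a local reaction.
4. Add a summary of worst post-baseline severity per subject, to be read alongside application-site AEs.

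Do not make the dosed-only table the main display. It removes reactors who paused, undosed subjects who still report symptoms and, if a blank diary is treated as not dosed, subjects who applied the gel but did not record it.

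The cost is one derived variable, small cell counts and a longer table. Dosing, visits and data collection do not change.
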